3.1 General Design

[figure not shown]
Tau and A β PET scanning takes place at the Kreitchman PET Center in the Radiology Department at Columbia University on separate days within 24 months of each other. ^{18}F -MK-6240 will be provided by Cerveau and ^{18}F -Florbetaben is provided by Life Molecular Imaging. Participant preparation includes intravenous catheterization followed by administration of 8.1 mCi as a slow single intravenous bolus (6 sec/mL) in a total volume of up to 10 mL of ^{18}F -Florbetaben for A β PET imaging and 5 mCi of ^{18}F -MK-6240 for tau PET. The ^{18}F -Florbetaben PET scans are acquired over a period of 20 minutes in 4×5 minute frames on an MCT PET/CT scanner (Siemens) in dynamic, 3D imaging mode beginning 90 minutes after injection. The ^{18}F -MK-6240 PET scans are acquired over a period of 30 to 60 minutes in 6×5 to 12×5 minute frames on the same scanner, beginning 60 to 80 minutes after injection.

Transmission scans are done prior to the emission scan. An accompanying structural CT scan (in-plane resolution=0.58 \times 0.58 mm, slice thickness=3mm, FOV=29.6 \times 29.6 cm, number of slices=75) is also acquired. For quantitative analysis of tau and A β PET scans[20], dynamic PET frames are aligned to the first frame with rigid-body registration and a static PET image is obtained by averaging the four frames. The static PET image is then registered to the CT to obtain the inverse transformation matrix that transfers the CT image to the static PET image space. Each individual's MPRAGE MRI is also registered to the participant's CT image using normalized mutual information and tri-linear interpolation. Sets of regions-of-interest (ROIs) are selected from the FreeSurfer (FS)-segmented MRI scans. A combination of the two transformation matrices is used to transfer the ROI masks and the cerebellar grey matter from MRI space to static PET image space using nearest neighbor interpolation. These regional masks are used to extract the regional PET data. The SUV, defined as the decay-corrected brain radioactivity concentration normalized for injected dose and body weight, is calculated in selected regions. The SUV is then normalized to cerebellum grey matter to derive the SUVR. This process is illustrated in Figure 6.

For tau PET, in asymptomatic individuals tau pathology is typically restricted primarily to the medial temporal lobes [21-24] (corresponding to Braak Stage I/II) and tau pathology in this region appears to be selectively related to episodic memory [23, 24], so we will use bilateral medial and inferior temporal cortex for the primary analysis of tau imaging. We will also quantitate SUVR in regions corresponding to Braak stage III/IV (limbic cortex), and stage V/VI (isocortex) [23] for secondary analyses. Tau SUVR data in all FreeSurfer-defined cortical regions will be databased for exploratory analyses.

For A β PET, SUVR values are derived in lateral temporal cortex, parietal cortex, and posterior

Figure 6. Procedures for PET quantification

cingulate/precuneus as the primary ROIs. Using K-means clustering of log-transformed SUVR values, we derive cut scores for positivity following established procedures[25]. The overall rating is A β + if any of the regions is considered positive. For the current study we are primarily concerned with whether participants are A β +, but we will also database continuous amyloid SUVR values in all FS-defined ROIs.

3.2 Primary Study Endpoints

The primary outcome measure will be regional SUVR values for ^{18}F -MK-6240 and A β + for ^{18}F -Florbetaben.

3.3 Primary Safety Endpoints

The PET/CT imaging in this study is being undertaken for research purposes only and will not be reviewed clinically unless specifically requested. The majority of participants will receive or have received an MRI scan under a different protocol, which is reviewed clinically. A small number of participants are not eligible to receive an MRI scan due to contraindications, and therefore will not have had a clinical review.

4 Subject Selection and Withdrawal

4.1 Inclusion Criteria

We will limit our recruitment into this study to people who are between 35 and 85 years old at the time of enrollment, with or without confirmed WHICAP parent history of AD, and who are currently enrolled in the ongoing Offspring Study. Recruitment will focus on those individuals who did or will undergo structural MRI scanning as part of this Offspring study within 18 months of PET study participation. A small number of subjects who enroll in the PET study may have contraindications to MRI scanning, for which we have an adjusted method of image analysis in place as described in Section 4.3 below.

The participants must meet the following:

1. Age 35-85 years
2. Have either mild cognitive impairment or mild clinical Alzheimer's disease; or have no problem with memory or thinking
3. Able to participate in all scheduled evaluations and to complete all required tests and procedures
4. Must be considered likely to comply with the study protocol and to have a high probability of completing the study

4.2 Exclusion Criteria

Exclusion criteria include pregnant or lactating women, conditions precluding entry into the scanners (e.g. claustrophobia, etc.), and inability to have a venous catheter for the injection of the radioligand.

CONFIDENTIAL

This material is the property of Columbia University Medical Center. Do not disclose or use except as authorized in writing by the study sponsor.

Participants will be excluded from the study if any of the following applies:

1. Past or present history of certain brain disease other than mild cognitive impairment or mild clinical Alzheimer's disease
2. Certain significant medical conditions. Examples are uncontrolled epilepsy or multiple serious injuries
3. Unable to lie still for the duration of the PET scans
4. Radiation exposure for research studies in the last year that would put the subject past allowable limits if included in this study
5. Participation in the last year in a clinical trial for a disease modifying drug for AD unless it can be determined that the subject received a placebo and not an active drug
6. Conditions that preclude entry into the scanner (e.g., claustrophobia, etc.).
7. Inability to have a catheter placed in the vein for the injection of the dye
8. Currently pregnant or breastfeeding

4.3 Subject Recruitment and Screening

Adult children from the WHICAP study are currently being recruited into the Offspring Study. The parents are a selected subset of participants in WHICAP who are active (seen at the most recent assessment wave) or inactive (deceased, moved, too ill to participate) and seen at baseline and at least one follow-up. We recruit from families in which parents with and without AD are demographically matched. Table 6 shows the number of WHICAP families from which we are recruiting offspring, given the current prevalence of AD among WHICAP participants and the expected conversion rate over 5 years among active participants. Our preliminary data suggest that on average, we will have access to two to three offspring who live in the greater NYC area.

We plan to assess 600 offspring per year for all five years of the Offspring Study, and obtain medical, neuropsychological, and functional data from an in-person visit. We are recruiting approximately 33% of the offspring to participate in brain MRI. These 1,000 (n=200 per year)

offspring will be representative of the cohort at large with respect to parent diagnosis, race/ethnicity, and sex. All offspring will be screened for eligibility for structural brain MRI. Table 6 shows our expected MRI recruitment based on our experience in the WHICAP study, our pilot interview data of offspring, and conservative estimates of eligibility and willingness

to be scanned. Only one offspring per family will be recruited for the MRI. If there are more than one offspring who are eligible for MRI within a family, we select the oldest. Of eligible families, we expect that 75% of offspring will be eligible after screening for MRI contraindications, and of those, 60% will be willing to participate (willingness rate was 79% in our survey), and thus we will have 1,079 eligible and willing MRI participants.

CONFIDENTIAL

This material is the property of Columbia University Medical Center. Do not disclose or use except as authorized in writing by the study sponsor.

A β and tau PET scans will be obtained on a representative subset of 150 offspring (with and without positive family history of AD) between the age of 35 and 85. We will prioritize individuals who have already undergone or will undergo structural MRI as part of the Offspring Study. We will obtain both PET scans within 24 months of each other. Therefore, about 33 individuals per year will be recruited and scanned for contemporaneous A β and tau PET and MRI scanning. MRI scans will be completed up to 18 months prior to the first PET scan, or up to 18 months after the last PET scan. Since MRI scanning has already commenced in the overall study, we will re-acquire MRI scans (with other funds) in instances when the initial scan falls outside of the 18-month window. A subset of PET eligible subjects may be ineligible for MRI scans due to contraindications. To allow us to continuously meet recruitment goals, we will still obtain PET scans on these individuals and use an adjusted statistical method during data analysis. Specially, PET data collected without MRI data will be quantified as parametric standard uptake value ratio (SUVR) images using atlas-based regions of interest (ROIs) rather than subject-specific, MRI-based ROIs. The Montreal Neurological Institute (MNI) brain atlas will undergo a non-linear spatial transform to PET space. An inferior cerebellar gray matter ROI from the MNI template will be used as reference region. Alzheimer's disease specific ROIs from the MNI template will be used to derive mean SUVRs. A covariate for analysis method (atlas-based ROIs vs subject-specific, MRI-based ROIs) will be included in all statistical analyses.

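### Minor: amyloid labels for participants without MRI may come from a different SUVR scale, and the planned method covariate cannot correct a label once it is used as the moderator

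*Combined protocol and SAP*

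**What the plan says.** **With MRI (section 3.1, General Design).** "Sets of regions-of-interest (ROIs) are selected from the FreeSurfer (FS)-segmented MRI scans", and "The SUV is then normalized to cerebellum grey matter to derive the SUVR". The primary amyloid regions are lateral temporal cortex, parietal cortex and posterior cingulate/precuneus. On the cut: "Using K-means clustering of log-transformed SUVR values, we derive cut scores for positivity following established procedures". A participant is Aβ+ "if any of the regions is considered positive". On continuous values the section adds: "we will also database continuous amyloid SUVR values in all FS-defined ROIs".

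**Without MRI (section 4.3, Subject Recruitment and Screening).** "An inferior cerebellar gray matter ROI from the MNI template will be used as reference region". The target regions are named only by type: "disease specific ROIs from the MNI template will be used to derive mean SUVRs". The one stated adjustment is: "A covariate for analysis method (atlas-based ROIs vs subject-specific, MRI-based ROIs) will be included in all statistical analyses".

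**Use of the label.** Section 3.2 makes Aβ+ a primary outcome measure. The Study Summary, section 2 and section 7.2 also make it the moderator of the tau associations. Section 2 defines the vascular aim through MRI markers of small-vessel disease. Sections 3.3 and 4.1 expect few participants without MRI and give no count.

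**The concern.** Both parts of the ratio differ between the two groups: the target masks and the reference region. If the pipelines give systematically different SUVRs, a cut suited to one scale is misplaced on the other. The text does not say which cut atlas-based values face. The any-region rule adds to the exposure, since an upward offset in one of three regions is enough to turn a negative participant positive.

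A method covariate works on model terms. It can absorb a shift in a continuous SUVR, or a difference in positivity rate when Aβ+ is the outcome. It cannot reclassify a person, and it does not enter the label-by-tau product term. At stake is one stated objective: whether the tau associations depend on amyloid status.

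**Working it through.** The plan gives no figure on this point to reproduce. N = 150 is from section 7.1. SUVR centres, SDs, the offset, the number without MRI and the true interaction are all assumptions.

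**1. One region, by hand.** Assume mean SUVR 1.1 (negative) and 1.5 (positive), log-SD 0.07, and the cut midway on the log scale. The distance from the negative mean to the cut is ln(1.5/1.1)/2 = 0.155. For a log shift d, the share of true negatives called positive is 1 − Φ((0.155 − d)/0.07).

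- d = 0: 1 − Φ(2.21) ≈ 0.013
- d = 0.05: 1 − Φ(1.50) ≈ 0.067
- d = 0.10: 1 − Φ(0.79) ≈ 0.215

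With 15 people without MRI and 20% positive there are 12 negatives. The expected false positives rise from 12 × 0.013 = 0.16 to 12 × 0.215 = 2.6 at d = 0.10. In a simulation on these inputs, with 10% of participants atlas-based and the method covariate included, an interaction of 0.60 is estimated as 0.564 with no shift and 0.527 at d = 0.10, a further loss of 0.037/0.564 = 7%.

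**2. Three regions with the any-region rule.** Simulation with N = 150 and 2,000 replicates:

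- regional correlation 0.7; centres 1.12 and 1.55; log-SD 0.05 or 0.07 in negatives and 0.12 in positives;
- a 2-means cut per region from MRI-based values;
- true interaction −0.5, residual SD 1, method covariate in the model.

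Prevalence starts at Table 4's healthy-volunteer rate, 26/188 = 13.8%. Because this study also enrols people with impairment, 25% and 40% were added. These correspond to mixes of about 27% and 62% MCI at Table 4's MCI rate (28/50 = 56%), e.g. (0.25 − 0.138)/(0.56 − 0.138) = 0.27.

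Results for 15 without MRI, offset 0 to +10% (the two values are for log-SD 0.05 / 0.07):

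| Aβ+ | Mislabelled among the 15 | Interaction | Further attenuation |
|---|---|---|---|
| 13.8% | 0.07 to 1.61 / 0.36 to 3.58 | −0.492 to −0.468 / −0.457 to −0.415 | 5% / 9% |
| 25% | 0.12 to 1.25 / 0.29 to 2.74 | −0.484 to −0.474 / −0.470 to −0.450 | 2% / 4% |
| 40% | 0.21 to 0.93 / 0.32 to 2.03 | −0.478 to −0.475 / −0.472 to −0.463 | 1% / 2% |

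The largest movement is 0.042 against an SE of 0.22, or 0.19 SE. Repeat simulations of the design ranged more widely. One gave 1-10% and 0.04-0.18 SE. The least favourable, at 13.8% positive and log-SD 0.07, moved from −0.454 to −0.395 with SE about 0.24: 0.059/0.454 = 13% and 0.059/0.24 = 0.25 SE, with Monte Carlo error of about 2 percentage points. Adding within-person log noise of 0.04 gave −0.449 to −0.385, about 14% and 0.27 SE, which is within that error of the previous run.

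**3. Milder inputs.**

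- 15 people, +5%: 0.1-0.9 extra mislabelled, 0-3% attenuation (13.8-25% positive).
- 8 people, +10%: 0.6-1.8 and 1-5%.
- 8 people, +5%: at most 0.5 and under 2%.
- 15 people, −10%: under 1% attenuation at 13.8-25% positive, about 2% at 40%.

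**4. What the covariate does.**

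- Label as moderator: the interaction with and without it differs by at most 0.002.
- Aβ+ as outcome, with two groups that differ 3:1 in the odds of lacking MRI and a +10% offset: the group risk difference is 0.106 with no offset, 0.120 with the offset and no covariate, and 0.105 with the covariate.
- Continuous tau, with a 10% scale difference and 20% without MRI: the slope ratio with the covariate is 0.978-1.017.

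**The case against.** The strongest reply is that section 3.1 sets one amyloid procedure for the study, and section 4.3 changes only how regions are delineated and which reference is used. On that reading the three regions, the K-means cut and the any-region rule carry over. This is a fair reading, and the remark about storing FreeSurfer-defined values is weak evidence against it. The section also defers to a cited procedure that cannot be checked from the documents. But a common rule does not remove the difficulty: one cut would still be applied to values from two pipelines.

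It is also fair that no harm is shown. Inferior cerebellar grey lies within cerebellar grey, so the references overlap. Few people are expected to lack MRI, and recruitment prioritises those who have it. With no offset at all, the clustering rule itself already attenuates the simulated interaction by 2-9%, much the same as the added loss. All this stands, and it is why the point is minor.

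A reader might infer that the whole moderation objective is compromised. The documents do not support that: section 2 ties the vascular aim to MRI markers, which people without MRI do not have, so they cannot enter that analysis or its amyloid moderation. Nor do the documents support inferring that the covariate is useless, given step 4 of the working.

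**Conclusion.** The point holds as a minor, cheap improvement. The method covariate is adequate for continuous tau and for Aβ+ as an outcome. It does not protect the Aβ+ label as moderator in the associations that people without MRI can enter: cognition and memory, olfaction, and race/ethnicity. With 15 of 150 without MRI and a +10% offset, about 1-3 extra people are mislabelled and the interaction is attenuated by about 1-13%, roughly 0.25 SE or less. With 8 people or +5% the effect is smaller still.

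These sizes rest on the assumed inputs. It would be too strong to say that labels will be wrong: the documents neither show that the pipelines differ in scale nor give the size or sign of any difference.

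**What to change.** 1. State that the atlas regions are the primary regions of section 3.1.
2. Process the existing scans of MRI holders through the atlas pipeline with its own reference region. Then either convert no-MRI values by the paired, region-by-region log-SUVR relation, or apply a cut derived from the atlas-processed MRI holders. Fix the choice before labels are examined.
3. Do not derive a cut from the no-MRI scans alone. At 13.8% positive and no offset, that mislabelled 1.5/2.2 of 15 people, or 1.9/2.1 of 8 (log-SD 0.05/0.07).
4. Keep the method covariate, report the number without MRI, and add a sensitivity analysis restricted to MRI-based quantification for the non-vascular associations.

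In simulation with 15 people, +10%, 13.8% positive and within-person log noise of 0.04, paired conversion cut the mislabelled from 3.2/4.6 to 0.2/0.7. The atlas-scale cut gave 0.2/1.0. The starting values exceed those in the table because of the added noise.

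**Cost.** SAP wording and extra processing of scans already acquired, about 135-142 participants; no new scans or participants. A random 40 would fix a mean regional offset to within 1.96 × 0.04/√40 = 0.012, about ±1.2%. One must assume that the paired relation carries over to people with MRI contraindications. The sensitivity analysis widens standard errors by about 3% with 8 excluded (√(150/142) = 1.028) and 5-6% with 15 (√(150/135) = 1.054; simulated 1.06).

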7.1 Sample Size Determination

The sample size of 150 subjects was selected to allow sufficient power ($\geq 80\%$) of a two-sided significance test with $\alpha = 0.05$ to detect meaningful effects associated with the primary hypotheses. We used the G*Power[28] to perform the following power analyses.

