7.2 Statistical Methods

Regional SUVR for ^{18}F -MK-6240 will be calculated to investigate associations with measures of memory, olfactory function, and cerebrovascular disease, and amyloid positivity for ^{18}F -Florbetaben will be calculated to investigate the potential moderation of amyloid on the associations with tau.

Before any specific statistical modelling techniques are applied, we will examine all variables for illegitimate values, outliers, and other inconsistencies. Distributions of demographic and other clinically important variables will be examined and summarized by means, standard deviations, minima, and maxima for continuous measures and proportions for categorical measures. Similar descriptive analyses will be conducted on all outcome variables of interest. We will make every effort to obtain all data to reduce or eliminate missing data issues. Tests will be two-sided and performed at a significance level of $\alpha=0.05$. After descriptive examination of the variables of interest, a series of unadjusted or partially adjusted planned analyses will be conducted to address the specific hypotheses, followed by fully adjusted models, follow-up analyses, and exploratory analyses. In all regression analyses, steps will be taken to avoid issues related to multicollinearity of the predictors. If necessary, data reduction techniques (e.g., screening out variables that are highly correlated) will be applied to the predictors prior to fitting the regression models.

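### Tau SUVRs from two image pipelines are pooled with one method covariate, which removes a constant shift but not a scale difference; the average bias is probably small, and calibration on existing scans would fix it cheaply

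*Combined protocol and SAP*

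**What the plan says.** Section 3.1 of the protocol describes the standard pipeline. "Sets of regions-of-interest (ROIs) are selected from the FreeSurfer (FS)-segmented MRI scans", and for the denominator, "The SUV is then normalized to cerebellum grey matter to derive the SUVR". The same section makes bilateral medial and inferior temporal cortex the primary tau region.

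Section 4.3 describes a second pipeline for participants who cannot have MRI. Their target regions come from the MNI template and are described only as specific to Alzheimer's disease. They are not listed or mapped to the primary tau region. The denominator also changes: "An inferior cerebellar gray matter ROI from the MNI template will be used as reference region".

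The two sets of values are analysed together, with one stated adjustment: "A covariate for analysis method (atlas-based ROIs vs subject-specific, MRI-based ROIs) will be included in all statistical analyses". Sections 7.1 to 7.3 add no method-by-tau interaction, no calibration between pipelines and no pipeline-specific sensitivity analysis.

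The number affected is given only in words. Section 3.3 says "A small number of participants are not eligible to receive an MRI scan due to contraindications", and section 4.1 is no more precise.

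**The concern.** For participants without MRI, both the numerator and the denominator of the SUVR are defined differently. A change of reference region multiplies the SUVR by a factor, so its effect grows with the tau level. A change of target region need not act proportionally, but nothing suggests that it produces only a constant shift. A main-effect covariate corrects the mean of the atlas group. If the two scales differ, it leaves high and low values misplaced relative to each other. Where tau is the predictor (memory, olfaction), the pooled slope then mixes two units of measurement. Where tau is the outcome (race/ethnicity), contrasts within the atlas group are stretched or shrunk.

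Method also coincides with having an MRI contraindication. The method coefficient therefore cannot be read as a pipeline effect, because it absorbs any real tau difference in those people as well.

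At stake is whether the participants kept in order to hold the sample size are measured on the same scale as the rest, and whether the plan has any means of showing it.

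**Working it through.** **The plan's own figure.** Section 7.1 says "The sample size of 150 subjects was selected to allow sufficient power" (at least 80%, two-sided 0.05) to "detect meaningful effects associated with the primary hypotheses". It gives no effect size or SD, so 150 cannot be reproduced. Back-solving for a correlation gives r = tanh((1.960 + 0.842)/√147) = 0.227, which is used below as the reference effect.

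**Inputs.**
- N = 150 (section 7.1).
- Number on the atlas method, n2: not stated. Assumed 5 to 15. As an upper bound, section 4.3 expects 75% of offspring to pass MRI screening; without any prioritisation that leaves 0.25 × 150 = 37.5, about 38.
- Scale factor k (atlas SUVR = a + k × MRI-pipeline SUVR): not stated. Assumed 0.7 to 1.2.
- n1 = 150 − n2. SUVR variance is taken as similar in the two groups unless stated otherwise.

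**Average bias that remains with the method covariate in the model.**
- Tau as predictor: slope ratio = (n1 + n2·k)/(n1 + n2·k²).
- Tau as outcome: coefficient ratio = 1 + (k − 1)·n2/150.

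| n2 | k | Tau as predictor | Tau as outcome |
|---|---|---|---|
| 5 | 0.7 | 148.5/147.45, +0.7% | −1.0% |
| 5 | 1.2 | 151/152.2, −0.8% | +0.7% |
| 15 | 0.7 | 145.5/142.35, +2.2% | −3.0% |
| 15 | 1.2 | 153/156.6, −2.3% | +2.0% |
| 38 | 0.8 | 142.4/136.32, +4.5% | −5.1% |
| 38 | 1.2 | 157.6/166.72, −5.5% | +5.1% |

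**Power.** In simulation (4,000 runs per setting, skewed SUVR, r = 0.227, k = 0.8 or 1.2, n2 = 8, 15 or 38), the covariate model has power of about 0.79 to 0.81. Calibration idealised as error-free gives about 0.80. Dropping the MRI-less participants gives 0.776 (n = 142) or 0.755 (n = 135).

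**One high-tau participant without MRI.** Section 1.4 reports SUVRs up to 4.0 in AD and about 0.5 to 1.5 in healthy volunteers. Suppose one atlas participant has 4.0 and everyone else averages 1.1 with SD s (assumed 0.20 to 0.35). The within-group sums of squares are S1 = (n1 − 1)s² and S2 = (n2 − 2)s² + ((n2 − 1)/n2) × 2.9². The slope ratio is (S1 + k·S2)/(S1 + k²·S2).
- s = 0.35, n2 = 5: S1 = 17.64, S2 = 7.10; +5.1% (k = 0.8), −6.1% (k = 1.2).
- s = 0.20, n2 = 15: S1 = 5.36, S2 = 8.37; +12.5% (k = 0.8), −11.5% (k = 1.2).

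**What calibration would deliver.** With 135 to 145 people processed both ways and a residual SD of 0.3 to 0.5 SUVR SDs (assumed), the SE of a standardised calibration slope is about 0.3/√144 = 0.025 to 0.5/√134 = 0.043. By comparison, a method-by-tau interaction estimated from 5 to 15 people would detect, with 80% power, only standardised slope differences of about 0.8 (n2 = 15) to 1.4 (n2 = 5).

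**The case against.** The best defence is that the protocol recognises the pipeline difference, prespecifies an adjustment, gives priority to people with MRI and expects few without. On average the adjustment then works well enough: bias of a few per cent and almost no loss of power. Section 7.2 also plans outlier checks and follow-up analyses, although none is aimed at the pipeline. This defence stands as far as size is concerned. It does not show that the two SUVRs are interchangeable.

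Some stronger readings are tempting but not supported:

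- **That a poorly estimated method coefficient spoils the tau result.** Its SE is √(1/n1 + 1/n2), or 0.46 to 0.27 SUVR SDs for 5 to 15 people. But it is a nuisance coefficient, and imprecision in it does not by itself bias the tau slope.
- **That the MRI-less participants add almost no information.** The power figures say otherwise.
- **That the reference tissue differs.** Both are cerebellar grey matter; the region differs. Section 3.1 does not say that the standard reference is the whole cerebellum.
- **That errors at SUVR 4.0 are typical.** That value is the top of the range in a study with three AD subjects. Neither the size nor the direction of a scale difference is given in the documents.
- **That the tau-cerebrovascular models cannot be run.** People without MRI have no MRI marker and drop out, so the covariate is constant there. The instruction to include it everywhere needs a wording correction; no result changes.

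The documents also do not say whether MRI ineligibility differs by race or ethnicity. If it does, the pipeline issue could matter more for that comparison.

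**Conclusion.** The concern holds as a modest weakness in the analysis method. Different target and reference regions are pooled, and the single stated covariate, read as a main effect, corrects a shift but not a scale. It also cannot tell a pipeline shift from a true tau difference in people with MRI contraindications.

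With 5 to 15 of 150 affected and a scale factor of 0.7 to 1.2, average bias in the tau coefficient is at most about 1% (5 people) to 3% (15 people). It reaches about 5%, for a 20% scale difference, only if roughly 25% lack MRI, which is hard to square with the small number that the protocol expects. A single high-tau participant without MRI could raise the slope error to about 5% to 12%, but that is an illustration, not a forecast. The counts, the scale factor and the SUVR spread are all assumptions. Nothing here overturns the main analysis. The case for change is that a better method is available at low cost.

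**What to change.** In section 4.3, with matching text in section 7.2:

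1. State the expected number of participants without MRI.
2. Define template regions that match the primary medial and inferior temporal region and, where possible, use the same cerebellar reference in both pipelines. Without this step, calibration would predict one anatomical region from another.
3. Run the atlas pipeline on the existing tau PET scans of every participant with MRI. Estimate the within-person calibration and use it to put the MRI-less SUVRs on the MRI scale. Carry the calibration uncertainty into the models, for example by multiple imputation. State the assumption that the calibration transfers to people with MRI contraindications, and whether the method covariate is then kept.
4. As sensitivity analyses, repeat the memory, olfaction and race/ethnicity models with atlas-based SUVR in everyone, and again in participants with MRI-based SUVR only.
5. State that the method covariate does not apply in the tau-cerebrovascular models, where nobody without MRI contributes.

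The cost is image processing and quality control for about 135 to 145 existing scans, the wording change, and slightly wider intervals from calibration uncertainty. No scans or participants are added.
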